5.7.4 Neutropenia and episode of neutropenic fever

To define **S2** (New episode of neutropenic fever within 28 days), we also need to define neutropenia. Start of neutropenia is defined as the time when neutrophil counts are first observed $< 0.5 \times 10^9$. Time of stop of neutropenia is defined as the first time neutrophil count is observed $\geq 0.5 \times 10^9$ after start time. An episode of neutropenic fever starts when the child is first observed with both neutropenia and fever. It stops when either fever or neutropenia stops (whichever comes first).

Durations of neutropenia expressed in days are computed as the time difference between two dates and times: that of neutropenia stop and that of neutropenia start. Hence, treatment durations expressed in days are not whole numbers, but decimal numbers. This definition of neutropenia is used to compute secondary outcome **S2** and some rates (See Sections 4.2).

6 Analysis Sets

- The “**All episodes analysis set**” consists of all randomized episodes.
- The “**Per protocol analysis set**” consists of all randomized episodes except those for which the child did not receive the “short” or “long” treatment strategy to which he or she was randomized. These children will be identified as detailed in Section 10.2.3.

7 Analyses supporting the primary objective

The main analysis supporting the primary objective and corresponding to the estimand detailed in Section 4.1 will use the “All episodes analysis set” and corresponds to an ITT analysis.

To estimate the between arm difference in means with a 95% confidence interval and a p-value, we will use a multiple linear model (aka ANCOVA). The model will be fitted via GEE [17] and the standard errors will be computed accordingly, to account for possible within-patient correlation, as already mentioned in Section 5.5. We will use an independent working correlation structure, as we expect the correlation to be negligible and because additional assumptions might be needed for other choices [24]. The variance and link functions that define the GEE will be that of a gaussian family with an identity link, as commonly used for quantitative outcomes. Baseline covariates included in the model will be:

²pricisely, that of fever stop or 28 days after treatment initiation, whichever comes first (because we compute the sum within 28 days).

- Age at randomization
- Type of cancer (“AML or Relapse ALL”, “ALL, in induction treatment”, “ALL, not in induction treatment” or “Other cancers”)
- Absolute neutrophil count (ANC) at presentation (≤ 0.1 , $]0.1; 0, 5[$ or ≥ 0.5 ; unit is 10^9 cells/L)
- Thrombocyte count at presentation
- Study site (Copenhagen, Aarhus or Odense)

These variables will be included in the model in addition to the binary variable that indicate the randomized assignment to “short” or “long” treatment duration. No interaction will be used in the multiple linear model. To avoid unnecessarily strong linearity assumptions, the effects of age and thrombocyte count will be modelled via linear splines, with two knots at 6 and 13 years for age and two knots at 50×10^9 cells/L and 100×10^9 cells/L for thrombocyte count. An example of R code corresponding to this analysis is provided in appendix A.1.

8 Analyses supporting secondary objectives

The main analysis supporting the secondary objectives and corresponding to the estimands detailed in Section 4.3 will use the “All episodes analysis set” and corresponds to an ITT analysis [16].

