5.2 Statistical Hypotheses

The null hypothesis to be tested in relation to the primary estimand (detailed in Sec. 4.1) is as follows:

- **Null hypothesis:** the mean number of days alive without antibiotic treatment within 28 days after treatment started is **the same** when the children receive the “short” and “long” treatment duration strategies¹. Formally, $\mathcal{H}_0 : \mu_1 = \mu_0$, where μ_1 and μ_0 are the mean number of days when the children receive “short” and “long” treatment duration strategies, respectively.

versus

- **Alternative hypothesis:** the mean number of days alive without antibiotic treatment within 28 days after treatment started is **different** when the children receive the “short” and “long” treatment duration strategies¹. Formally, $\mathcal{H}_1 : \mu_1 \neq \mu_0$.

We will use a two-sided test at 5% and matching 95% two-sided confidence interval (CI).

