5.5 Within-patient correlation between episodes

A child can be randomized more than once and consequently a child can contribute with more than one episode. Bone marrow recovery and subsequent chemotherapy treatment must have taken place before a new randomization of the same child can occur, as detailed in the protocol. We cannot rule out that the outcome from two episodes from the same patient are more likely similar than the outcome of two episodes from two different patients. That is, we cannot rule out within-patient correlation between episodes. To analyze the data accordingly, we will use Generalized Estimating Equations (GEE) [17] as implemented in the popular geepack package of R [13]. Standard errors will be computed via either a standard “sandwich” approach, as implemented in geepack, or non-parametric cluster bootstrap [4, Sec. 3.8] (see Sections 7 and 8).

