10.1.4 Subgroup analyses

There is only one pre-specified subgroup analysis.

- episodes with ANC at presentation $\leq 0.1 \times 10^9$ cells/L, i.e., episodes of patients considered at “very high” risk.

We will replicate the main analysis of the primary outcome described in Section 7, up to minor differences for the baseline covariate adjustment. Specifically, for any baseline categorical variable, a group of less than five episodes will be combined with the smallest group of more than five episodes. Similarly, we will also drop knots if the subgroups that they implicitly define do not

all contain at least than five episodes (0-5, 6-12 and ≥ 13 years for age and 0-49, 50-99, ≥ 100 for thrombocyte, in 10^9 cells/L unit). We will also replicate the analysis of main analyses of the secondary outcomes described in Section 8.

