11.2 Additional power calculations

After the decision to stop the trial early was taken, it has been anticipated that about 100 episodes would be included by the end of the trial. Below we provide the results of a standard power calculation [3, Sec. 3.2.1] for a sample size (i.e. number of episode, n) ranging from 90 to 110 (and $n=198$), assuming the same difference in means and standard deviation as for the initial sample size calculation detailed in Section 11.1 (and no dropout, as none were observed and dropouts were no longer expected).

Sample size (n)	90	95	100	105	110	198
Power	59%	62%	64%	65%	68%	90%

Further calculation suggest that, to get 90% power with a sample size of $n=100$ while assuming a standard deviation of 6.5 days, we would need to assume a difference in means of 4.3 days instead 3 days. Assuming a more modest difference in means of 3.5 days, the power is computed as 77%.

12 Changes to protocol-planned Analyses

1. Time to next chemotherapy is no longer a secondary outcome. It is no longer considered a secondary outcome of interest for two main reasons. First, it is influenced by numerous factors beyond infections, such as logistical and scheduling issues which introduces variability. Second, this outcome is essentially a proxy for the more relevant “Time to bone marrow recovery”, which already serves as a secondary outcome (**S5**) and more directly reflects patient recovery and treatment effectiveness.
2. Alterations in gut microbiome is no longer considered a secondary outcome. It is now considered as an exploratory outcome that will be analyzed later, hence this SAP does not pre-specify its analysis.
3. The initial statistical analysis plan mentioned a non-inferiority margin of 10% for the secondary outcomes analysis. This was not the results of carefully considerations and we will no longer consider this margin. It is irrelevant to non-binary secondary outcomes (**S3** and **S5**) and its clinical relevance in unclear for the analysis of binary outcomes (**S1**, **S2** and **S4**). Consequently, for the interpretation of the results, there will be no specific focus on whether the two-sided CIs contain a specific non-inferiority margin.

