# fit model
library(geepack)
geePrimary <- geeglm(days~ treat + age + age5 + age12
                      + cancer + anc + thrombo + thrombo50 +
                      thrombo100 + site,
                      data=d,                                # data set (long format)
                      id=id,                                 # patient ID (clusters)
                      family=gaussian("identity"), # usual linear model parametrization
                      corstr="independence")      # independent working correlation structure
summary(geePrimary)

```

In the above, the dataset "d" is assumed to include the following variables: "days" indicates the number of days alive without antibiotic treatment within the first 28 days, "id" the patient ID (clustering variable), "treat" the randomized treatment strategy, "age" the age at randomization, "cancer" the type of cancer, "anc" the absolute neutrophil count at presentation, "thrombo" the thrombocyte count at presentation and "site" the study site.

A.2 R code for secondary binary outcomes S1 and S2 analysis

```
library(geepack)
geeBinary <- geeglm(Y~treat,
                      data=d,
                      id=id,
                      family=binomial("log"),
                      corstr="independence")
#--- extract estimate and SE (log-scale) -----
logRR <- summary(geeBinary)$coef["treat","Estimate"]
SElogRR <- summary(geeBinary)$coef["treat","Std.err"]
#--- compute Risk Ratio and 95% CI -----
Results <- exp(c(logRR,
                  logRR-qnorm(0.975)*SElogRR,
                  logRR+qnorm(0.975)*SElogRR))
```

In the above, the variable "Y" indicates the binary outcome of interest, "id" the patient ID (clustering variable) and "treat" the randomized treatment strategy.

A.3 R code for mortality analysis (S4)

```
library(exact2x2)
uncondExact2x2(x1=x1obs,
                n1=n1obs,
                x2=x2obs,
                n2=n2obs,
                parmytype="difference", # estimand is risk difference
                alternative = "two.sided", # two-sided CI wanted
                method="score", # score statistic ordering is used
                conf.level = 0.95, # 95% confidence level
                conf.int=TRUE) # computation of CI wanted
```

A.4 R code for secondary quantitative outcome S3

In the R code below, we assume that the dataset R contains the following variables:

- days: the outcome, a number of days corresponding to either S3 or S5.

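### With 15 coefficients on about 100 episodes, the uncorrected GEE sandwich standard error makes the nominal 5% primary test run at about 7 to 8%

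*SAP*

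**What the plan says.** Section 5.2 commits the trial to a two-sided 5% test with a 95% interval to match. Section 5.3 makes this the only formal hypothesis test.

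Section 7 specifies a Gaussian, identity-link linear model: "The model will be fitted via GEE [17] and the standard errors will be computed accordingly, to account for possible within-patient correlation". On the working correlation it says "We will use an independent working correlation structure, as we expect the correlation to be negligible". Section 5.5 allows two kinds of standard error, a standard sandwich "as implemented in geepack, or non-parametric cluster bootstrap". Section 8.2 assigns the bootstrap to S3 and S5, which leaves the sandwich for the primary outcome. Appendix A.1 agrees: the call begins "geePrimary <- geeglm(days~ treat + age + age5 + age12", sets no standard-error option, and takes the result from the model summary. The SAP names no small-sample correction, t reference or degrees of freedom.

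On size, Section 11.2 says "it has been anticipated that about 100 episodes would be included by the end of the trial". Section 5.5 notes that a child may contribute several episodes, so there may be fewer patients than episodes. Section 10.1.4 carries the same analysis into the subgroup with ANC at presentation of 0.1 or below: "We will replicate the main analysis of the primary outcome described in Section 7".

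**The concern.** With an independence working correlation and a Gaussian family, the point estimate is ordinary least squares. The uncorrected sandwich is built from fitted residuals. These are smaller than the true errors because the model has used up leverage fitting them. The more coefficients per episode, the greater the shrinkage and the smaller the reported standard error. Fifteen coefficients on about 100 episodes is enough for this to matter.

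What is at stake is the error rate of the single confirmatory claim and the width of the headline interval. A borderline result could be declared significant only because the standard error was too small. The authors are cautious about sample size elsewhere: Section 8.1 lists limited effective sample size among its reasons for not adjusting the binary outcomes, and drops GEE for mortality because its asymptotics would be doubtful. The primary analysis has no comparable safeguard.

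**Working it through.** **Inputs from the SAP.** Two-sided 5% (Section 5.2); SD 6.5 days and difference 16 − 13 = 3 days (Section 11.1); about 100 episodes, range 90 to 110 (Section 11.2); covariates (Section 7, Appendix A.1).

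**Inputs assumed, because the SAP does not give them.** Number of patients (50 to 100 for 100 episodes), within-patient correlation (ICC 0 to 0.3), covariate distributions, subgroup size.

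**The plan's own figures.** Sample size: 2 × 6.5² × (1.96 + 1.282)² / 3² = 98.7, so 99 per arm, 198 in total, and 198/0.9 = 220. Power at n = 100: the SE of the difference is 6.5 × √(4/100) = 1.3, and Φ(3/1.3 − 1.96) = 63.6%, against the stated 64%. These reproduce.

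**Coefficient count.** Intercept 1 + treatment 1 + age spline 3 + cancer type 3 + ANC 2 + thrombocyte spline 3 + site 2 = 15. If the ANC class of at least 0.5 is empty, as the population in Section 4.1 suggests it may be, the count is 14.

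**First-order check.** The variance is low by about 1 − p/n, so the true level is 2 × [1 − Φ(1.96 × √(1 − p/n))].
- p = 15, n = 100: √0.85 = 0.922; 1.96 × 0.922 = 1.807; level 7.1%.
- p = 15, n = 90: 7.4%. p = 15, n = 110: 6.9%. p = 14, n = 100: 6.9%.

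This step needs no assumption about ICC, patient numbers or covariates.

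**Null simulation.** 5,000 replicates per row (Monte Carlo SE about 0.4 points), site-stratified blocks, Section 7 covariates. The t reference uses patients minus coefficients as degrees of freedom. The scaled sandwich multiplies the SE by √[G/(G − 1) × (n − 1)/(n − p)], where G is the number of patients. Entries are rejection rates in %.

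| Episodes / patients / ICC | As planned (1.96) | t only | Scaled + t | CR2 + t | CR3 + t |
|---|---|---|---|---|---|
| 100 / 100 / 0 | 7.2 | 6.9 | 5.1 | 5.2 | 3.3 |
| 100 / 80 / 0.1 | 7.4 | 7.0 | 4.8 | 4.9 | 3.2 |
| 100 / 65 / 0.1 | 7.9 | 7.2 | 5.1 | 5.1 | 3.3 |
| 100 / 50 / 0.1 | 8.4 | 7.3 | 5.0 | 5.1 | 3.5 |
| 90 / 70 / 0.1 | 8.2 | 7.5 | 5.3 | 5.3 | 3.0 |
| 110 / 85 / 0.1 | 7.4 | 6.7 | 4.8 | 4.9 | 3.4 |
| 100 / 80 / 0.3 | 8.3 | 7.6 | 5.3 | 5.3 | 3.4 |
| 100 / 80 / 0.1, skewed outcome | 7.2 | 6.8 | 4.7 | 4.7 | 2.9 |
| 100 / 80 / 0.1, 14 coefficients | 7.7 | 7.2 | 5.4 | 5.3 | 3.7 |
| *198 / 150 / 0.1* | 6.2 | 5.9 | 4.8 | 4.7 | 3.9 |
| *100 / 80 / 0.1, treatment only* | 6.0 | 5.7 | 5.4 | 5.4 | 5.1 |

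The two italic rows are for comparison. In the other rows the mean sandwich SE is about 0.90 to 0.93 of the true SE, and 95% interval coverage is 91.6 to 92.8%. Simulations under other assumed covariate distributions gave 6.9 to 8.8%.

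**Subgroup.** The ANC factor drops out, leaving at most 13 coefficients. For an assumed 60 episodes, the first-order level is 2 × [1 − Φ(1.96 × √(1 − 13/60))] = 8.3%. Simulation with 48 patients gave 9.0%, which corresponds to interval coverage of about 91%.

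**The case against.** - **The inflation is moderate, and not all of it comes from the covariates.** A treatment-only model at 100 episodes gives 6.0%, and the full model at 198 episodes gives 6.2%. This stands: the combination of 15 coefficients with about 100 episodes adds roughly 1 to 2 points to what a sandwich with a normal reference costs anyway. The total departure from 5% is still 2 to 3 points, and that is what Section 5.2 promises to control.
- **The exact figure rests on assumptions.** True of the simulations, but the first-order check does not use them, and every 14- or 15-coefficient scenario at 90 to 110 episodes exceeded 5%.
- **Section 5.6 appeals to robust type I error under randomization.** It does so in relation to parametric modelling assumptions. The simulated models were correctly specified and still exceeded 5%, so this is a different problem.
- **Section 7 expects negligible correlation.** The excess is present with one episode per patient and ICC 0.
- **Appendix A.1 is only an example, and reading its summary as a large-sample Wald test relies on knowledge of the software.** Section 5.5 names the standard sandwich independently of the code, and a t reference alone still leaves 6.7 to 7.6%.
- **The subgroup has no formal test.** Correct under Section 5.3. The consequence there is an interval that is too narrow, not a false claim of significance.

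**Conclusion.** The point holds. As written, the primary test does not run at 5%. Its level is about 7 to 8% and the 95% interval covers about 92 to 93%, with an SE roughly 7 to 10% too small. The 7.1% first-order figure needs only 15 coefficients and 100 episodes. The simulated range depends on assumed patient numbers, ICC and covariate distributions, but neither its direction nor its approximate size changed across those tried. The point estimate, estimand and analysis set are unaffected. Because this is the trial's only formal test and the correction is simple, it should be fixed before the outcome is analysed.

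**What to change.** In Sections 5.5 and 7, replace the standard sandwich for the primary analysis with a pre-specified small-sample version, and use it for both the p-value and the 95% interval. Either a bias-reduced cluster sandwich (CR2, Kauermann-Carroll type) or the degrees-of-freedom-scaled sandwich will do. Take the reference from a t distribution with degrees of freedom equal to patients minus coefficients. The two performed alike (4.7 to 5.3% and 4.7 to 5.4% at 90 to 110 episodes). CR3 (Mancl-DeRouen) with t is valid but conservative, at 2.9 to 3.7%. A t reference alone is not enough. Carry the same choice into Section 10.1.4, and amend Appendix A.1 so that the code produces it. The covariates can stay as they are.

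The cost is a change of wording and code, and a wider interval. With 80 patients, t on 65 degrees of freedom is 1.997, so the width grows by about (1.997/1.96)/0.922 = 1.105, or about 10%. At a 3-day difference and SD 6.5, with non-prognostic covariates assumed, simulated power falls from about 63% to about 56%. Part of that loss was never real, since the uncorrected test rejects too often under the null as well. Section 11.2 should say that its 64% is not the power of the corrected test. The amendment should be dated before any comparison of the primary outcome by arm, since a later change of standard error could look data-driven.

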A.4	R code for secondary quantitative outcome S3	24

1 Statistical analysis plan approval signature page

Person writing the SAP:

Name: [name]

Position/Title: Associate Professor in Biostatistics

[figure not shown]
January 13, 2025

Signature & Date

Approved by:

Name: [name]

Position/Title: MD PhD, Senior Consultant

January 15, 2025

Signature & Date

Name: [name]

Position/Title: MD, PhD, Associate Professor, Senior Consultant

15-01-2025

Signature & Date

2 List of Abbreviations

- ALL: Acute Lymphoblastic Leukemia
- AML: Acute Myeloid Leukemia
- ANC: Absolute Neutrophil Count
- ANCOVA: Analysis of covariance
- CI: Confidence Interval
- GEE: Generalized Estimating Equations
- ITT: Intention-To-Treat
- SAE: Severe adverse event
- SAP: Statistical Analysis Plan

3 Introduction

This document is the statistical analysis plan (SAP) for an open label, investigator-initiated, parallel group, 1:1 randomized, multicenter, clinical trial of “short” versus “standard” (i.e., “long”) empirical antibiotics treatment duration of febrile neutropenia in high-risk children with cancer. Included children have an absolute neutrophil count (ANC) $< 0.5 \times 10^9$ cells/L and an expected duration of neutropenia of more than seven days. The primary endpoint is the number of days without antibiotic treatment within the first 28 days after treatment initiation. It is hypothesized that a “short” empirical antibiotics treatment duration is sufficient to prevent reinfection that would require additional antibiotic treatment days, hence superior to “standard” treatment duration. Randomization was stratified by site, via block randomization with random block size. Patient accrual has stopped early because of lower accrual rate than anticipated, as detailed in Sec. 3.1.

This SAP has been written after this decision to stop the trial early was taken. The changes to the protocol-planned analyses are summarized in Section 12. We do not consider them as major changes and the rationale for each of them is provided.

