The primary clinical question of interest is: *“Is the mean number of days alive without antibiotic treatment, within 28 days after treatment started, larger when children receive the “short” treatment duration strategy than when they receive the “long”, among children with cancer who started antibiotic treatment for high risk neutropenic fever of unknown origin, regardless of any intervention”*

during the follow-up needed to ensure good clinical care?

Accordingly, the primary estimand is described by the following attributes:

- Population: children (aged 0-17) with cancer receiving antibiotic treatment for high risk neutropenic fever of unknown origin 48 hours after presentation. In particular, children with
 - a single temperature of at least 38.5° C , or a temperature above 38.0° C sustained over a 1-hour period (auricular, oral or rectal), at presentation.
 - an absolute neutrophil count $< 0.5 \times 10^9$ cells/L and an expected duration of neutropenia of more than 7 days at presentation.
 - a negative blood culture (or other clinically relevant culture) 48h after the start of the culture.
- Endpoint: number of days alive without antibiotic treatment within the first 28 days after treatment initiation.
- Treatment: The investigational interventions (“short” vs “long”, as defined above) regardless of adherence and of any subsequent treatment decision or intervention during the follow-up needed to ensure good clinical care (“treatment policy strategy”, see [14]).
- The intercurrent event “any subsequent treatment decision or intervention needed to ensure good clinical care” is addressed by the treatment condition of interest attribute (“treatment policy strategy”, see [14]). The intercurrent event adherence to the investigational intervention is also addressed by the treatment condition of interest attribute (“treatment policy strategy”, see [14]). There are no other relevant intercurrent events anticipated.
- Population-level summary: Difference in means between treatment conditions.

Remarks:

- (i) The “treatment policy strategy” for the intercurrent event “adherence to the investigational intervention” is consistent with an Intention-To-Treat principle/analysis discussed in Section 5.1. In our context, “adherence” is defined as “continue antibiotic treatment” as long as defined by the treatment strategy (not shorter, not longer).

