4.2 Secondary endpoints

There are five secondary outcomes:

S1: Severe adverse event (SAE) within 28 days, defined as any of these events:

- Severe sepsis, defined as either (i) vasoactive treatment requirement or (ii) fluid bolus requirement $>20\text{mL/kg}$ or (iii) respiratory support requirement (mechanical ventilation).

- Fever with positive blood culture. For possible contaminants, at least two positive culture bottles were required. Possible contaminants include coagulase negative staphylococcus, micrococcus spp., non hemolytic streptococcus, Corynebacterium spp, Propionibacterium spp, Bacillus spp.
- Severe focal infection highly suspicious of bacterial cause, requiring antibiotic treatment (e.g. lungs, abdomen, CNS, skin)
- Death

S2: New episode of neutropenic fever within 28 days.

S3: Days alive without fever within 28 days.

S4: Mortality within 28 days.

S5: Time to bone marrow recovery (up to 3 month), defined as the time from start of treatment to first absolute neutrophil count (ANC) $\geq 0.5 \times 10^9$ cells/L.

Note: see Section 5.7 for details about the definitions of fever, neutropenia/neutropenic, **S2** and **S3**.

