5.7 Pivotal definitions

5.7.1 Time zero

To define many outcomes, e.g., **S2**: “new episode of neutropenic fever within 28 days”, we need to precisely define when the time starts. This is necessary to properly define the time window, e.g. “within 28 days”. In this SAP, we define that time (i.e., time zero) at the time of treatment initiation, not at time of randomization, which should occur appropriately 48 hours later. This is consistent with the definition of the primary outcome (see Section 4.1) and it should facilitate the interpretation of the results.

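### Section 7 provides a covariate level for ANC of 0.5 or more at presentation, which the Section 4.1 population excludes, and S5 as worded would score any such child as recovered before neutropenia begins

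*SAP*

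**What the plan says.** ANC is in units of 10⁹ cells/L throughout.

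- **Population (SAP Section 4.1).** The primary estimand concerns children with "an absolute neutrophil count $< 0.5 \times 10^9$ cells/L and an expected duration of neutropenia of more than 7 days at presentation".
- **Primary model (Section 7).** One of the baseline covariates is "Absolute neutrophil count (ANC) at presentation", given with its levels as "Absolute neutrophil count (ANC) at presentation (≤ 0.1 , $]0.1; 0, 5[$ or ≥ 0.5 ; unit is" 10⁹ cells/L. The model is fitted to all randomized episodes and is said to correspond to the Section 4.1 estimand.
- **S5 (Section 4.2).** Time to bone marrow recovery is "defined as the time from start of treatment to first absolute neutrophil count (ANC") at or above 0.5. No earlier count below 0.5 is required.
- **Time zero (Section 5.7.1).** "we define that time (i.e., time zero) at the time of treatment initiation, not at time of randomization".
- **End of neutropenia (Section 5.7.4).** This is the first count of 0.5 or more that follows the start of neutropenia. The section applies the definition to S2 and some rates and does not mention S5.
- **Baseline table (Section 10.2.2).** ANC at presentation and the minimum ANC from presentation to randomization are listed as two separate variables.

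**The concern.** The population attribute and the covariate refer to the same measurement at the same time point, and they disagree on the values it can take. Either the model names a level that no eligible episode can occupy, or some randomized episodes fall outside the population that the estimand describes.

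The second case would carry over to S5. A child who presents with a count of 0.5 or more and becomes neutropenic a day or two later already meets the S5 event criterion when the clock starts. Such a child would be recorded as recovered while bone marrow suppression was still developing. That pulls down the median time to recovery in whichever arm the child belongs to. It also gives a reported value that does not mean what the endpoint's name says.

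**Working it through.** No figure in the plan depends on this point, so the check is mainly a comparison of definitions, followed by an illustration of size.

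**Step 1. Do the two ANC definitions overlap?** Section 4.1 allows values below 0.5 at presentation. The Section 7 levels are: up to 0.1; strictly between 0.1 and 0.5; and 0.5 or more. The first two levels together cover everything below 0.5. The third is the exact complement and shares no value with the Section 4.1 population. Because the middle interval is open at 0.5 and the third level begins there, a slip in text extraction is an unlikely explanation.

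**Step 2. Is the third level likely to be filled?** The SAP gives no count. Listing a minimum ANC up to randomization as well as ANC at presentation makes sense if counts could still fall in that window. This is an inference only.

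**Step 3. What does S5 give for such a child?** The event is the first ANC of 0.5 or more, counted from treatment start.
- If the presentation sample counts as the observation at time zero, S5 is 0.
- If only samples after treatment start count, a child still at 0.5 or more at the next sample is scored as recovered then, before neutropenia.

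The interval-censoring method in Section 8.2 does not repair this, because it takes the event as defined.

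**Step 4. How far would an arm's median move?** If a share p of episodes is scored at 0, the overall median is the q-quantile of the remaining episodes, where q = (0.5 − p)/(1 − p).
- p = 5%: q = 0.45/0.95 = 0.474
- p = 10%: q = 0.40/0.90 = 0.444

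The SAP gives neither p nor the distribution of recovery times, so both are assumed.

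| Assumed recovery time in the other episodes | p = 0 | p = 5% | p = 10% |
|---|---|---|---|
| Gamma, shape 4, scale 3.5 | 12.85 d | 12.42 d | 11.94 d |
| Lognormal, median 12 d, log-SD 0.5 | 12.00 d | 11.61 d | 11.19 d |

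The falls are 0.43 and 0.91 days (gamma) and 0.39 and 0.81 days (lognormal), so about 0.4 to 0.9 days. The result depends on the assumed spread. With the lognormal log-SD at 0.3 the medians are 11.76 and 11.51 days (falls of 0.24 and 0.49). With log-SD 0.8 they are 11.38 and 10.73 days (falls of 0.62 and 1.27). With p = 0 there is no effect.

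**Step 5. Does this bias the comparison of arms?** ANC at presentation is fixed before randomization, so the expected share of such episodes is the same in both arms. In a simulation with the gamma distribution and 50 episodes per arm, scoring 0%, 5% or 10% at zero in both arms left the mean difference in medians at about 0. Its standard error rose from about 1.6 to 1.7 and 1.8 days.

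**The case against.** The strongest reply is that the third level is harmless. The analysis set is every randomized episode, which can include one that missed an eligibility criterion, and a covariate covering the full range gives that episode a category. An empty level carries no information on the treatment effect, and a filled one is a legitimate prognostic group. This stands: neither removing the level nor merging it is shown to improve the primary analysis, and Section 5.6 rightly relies on randomization for type I error control.

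A second reply is that S5 is consistent under the stated population, and that its name and the example in Section 5.4 (a child seen below 0.5 and later at or above it) make the intent clear. The intent is indeed clear, but the definition does not secure it. Section 5.7.4 contains the needed condition and applies it elsewhere.

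A reader might also infer more than the text supports:
- **That Section 3 contradicts the covariate too.** It does not. It says "Included children have an absolute neutrophil count (ANC") below 0.5 but names no time point, so the conflict rests on Section 4.1 alone.
- **That the S5 treatment difference is biased.** Step 5 shows only somewhat more random variation, which the planned cluster bootstrap is meant to reflect, and S5 carries no formal test (Section 5.3).
- **That such children were certainly enrolled.** The SAP never says so, and the exact eligibility time point may be fixed in the protocol, which is not at hand.

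**Conclusion.** The conflict between Sections 4.1 and 7 is explicit and needs to be reconciled. The S5 definition has a gap that matters only if the third ANC level contains episodes. In that case the population attribute fails to describe the analysed episodes, and the S5 medians are too low, by about 0.4 to 0.9 days for an affected share of 5% to 10%. That size rests on an assumed share and on two assumed distributions, and a different spread changes it. If there are no such episodes, S5 is unaffected and only the wording is inconsistent. The primary treatment comparison and the sample size and power figures are untouched in either case.

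**What to change.** 1. Reconcile Sections 4.1 and 7. State at which time point, or in which window, an ANC below 0.5 had to be met, and make the population attribute and the ANC covariate levels agree with that statement. Which eligibility rule applied is for the sponsor to state from the protocol and the enrolment records.
2. Reword S5 in Section 4.2 as the time from start of treatment to the first ANC of 0.5 × 10⁹ cells/L or more observed after the first ANC below that value, and extend the Section 5.7.4 definition explicitly to S5. For a child already below 0.5 at presentation, nothing changes.

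The cost is a few words in the SAP and one line in the S5 derivation. No new data are needed, and the change does no harm if no such episode exists.
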